- **Process for Aim 1b:** MAGE is a metric of glycemic variability that can be measured from CGM, but not from infrequent (daily) monitoring. Thus, among CGM patients only, we will measure the six-month longitudinal change in 24-hr average MAGE. Upon computing each CGM patient's daily MAGE, we will use patient-level hierarchical modeling (generalized linear mixed models) to estimate the overall sixmonth longitudinal trend in MAGE.

Specific Aim 1c: Measure longitudinal change in daily coefficient of variation (C_v) of blood glucose in CGM

- **Hypothesis for Aim 1c:** The patient-level daily C_v of blood glucose will decrease over six months of CGM.
- **Process for Aim 1c:** Like that of MAGE, C_v of blood glucose is a metric of glycemic variability that requires near continuous monitoring. Thus, among CGM patients only, we will measure the six-month longitudinal change in daily C_v of blood glucose using the standard equation: $C_v = \sigma/\mu$. Once we have computed each CGM patient's daily C_v of blood glucose, we will use patient-level hierarchical modeling (generalized linear mixed models) to estimate the overall six-month longitudinal trend in C_v of blood glucose. Additionally, we will report the patient- and group-level distributions in daily blood glucose extrema (i.e., minimum and maximum).

Specific Aim 1d: Measure longitudinal change in overall blood glucose range and “time in range” ($\max \text{Range} - \min \text{Range}$) in CGM

- **Hypothesis for Aim 1d:** The patient-level daily blood glucose range will decrease and time in range (which is defined by glucose levels from 70 to 180) will increase over six months of CGM usage.
- **Process for Aim 1d:** Again, like MAGE and C_v , the blood glucose range is a metric of glycemic variability that is most meaningful with near continuous monitoring. So, among CGM patients only, we will measure the blood glucose range for the i th day as $\text{Range}_i = \max \text{HbA1c}_i - \min \text{HbA1c}_i$, and then use patient-level hierarchical modeling (e.g., generalized linear mixed models) to estimate the overall six-month longitudinal trend in HbA1c range.

Specific Aim 1e: Measure the effect of CGM vs. the standard finger-prick protocol on frequency of hypoglycemic events

- **Hypothesis for Aim 1e:** The patient-level six-month reduction in frequency of hypoglycemic events will be greater among those randomized to CGM than that among those randomized to control.

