- **Process for Aim 1e:** Measure the patient-level change in rate of hypoglycemic events as the patient-level slope of the six-month linear change in the so-called “intensity” (λ) of the estimated nonhomogeneous Poisson point process. Once we’ve computed each patient’s six-month linear change in λ , we will compare the distributions between randomized groups. Note that the motivation for measuring change in frequency as the slope of λ estimated from a non-homogeneous Poisson process is that it allows us to compare changes in frequency of hypoglycemic events between groups with different modes of monitoring (continuous vs daily).

Aim 2: Assess impact of CGM on healthcare utilization and cost

Specific Aim 2a: Measure the effect of CGM vs. standard finger-prick protocol on healthcare utilization

- **Hypothesis for Aim 2a:** The count of primary care, specialist, and emergency department visits or hospital stays over six months will be fewer among those randomized to CGM than that among those randomized to standard finger-prick protocol.
- **Process for Aim 2a:** For each patient, count their visits to a primary care provider or specialist or emergency department/hospital admission. Next, compare the distributions of visit counts between randomized groups using a Poisson test, aggregated as well as stratified by visit type. Other metrics for evaluating utilization may include: current HEDIS performance on diabetes and behavioral health measures, coding specificity for diabetes, emergency department visit per 1000 rate, overall and for patients with diabetes, and hospitalization per 1000 rate related to diabetes.

Specific Aim 2b: Measure the effect of CGM vs standard finger-prick protocol on cost

- **Hypothesis for Aim 2b:** The total variable cost associated with healthcare services/visits over six months will be fewer among those randomized to CGM than that among those randomized to standard fingerprick protocol.
- **Process for Aim 2b:** For each patient, measure total variable cost of associated healthcare services and visits. Then compare the distribution of costs between randomized groups using the Wilcoxon rank-sum test, a non-parametric analogue of Student’s *t*-test.

Aim 3: Qualitatively understand patient perspective of CGM

Specific Aim 3a: Record patients’ self-reported willingness to participate in a CGM pilot

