7.0 STATISTICAL ANALYSIS

This study is a parallel randomized control trial that will evaluate the impact of CGM versus a standard fingerprick protocol, between and within randomized groups. The primary analysis (Specific Aim 1a) will measure the intervention effect on six-month change in HbA1c. The quantitative secondary analyses will measure the withinpatient longitudinal change in glycemic variability among CGM patients (Aims 1b-d) as well as the intervention effect on hypoglycemic events, healthcare utilization and cost (Aims 1e, 2a-b) between randomized groups. Additionally, for each of these aims, we will conduct exploratory sensitivity analyses: measuring provider variability and its effect, as well as looking at patient-level heterogeneity of treatment effect (HTE) to describe

subgroups of patients in whom the benefit of CGM might be amplified or attenuated. Technical details are provided in Section 7.1 *Statistical Considerations*.

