7.1 Statistical Considerations

The primary analysis (Aim 1a) will measure the intervention effect on the patient-level six-month absolute reduction in mean HbA1c. Since not all patients will have their final HbA1c test at six months exactly, we will estimate each patient's six-month reduction in HbA1c by interpolating/extrapolating from their assessments, given that their HbA1c levels were assessed on at least two occasions: baseline, and >3 months post baseline. Then, among patients with a sufficient number of occasions of HbA1c assessments, we will estimate their sixmonth HbA1c using generalized linear mixed models with patient-level random slopes and intercepts, with appropriate link function and distributional family [8]. The quantitative secondary analyses (Aims 1b-e, 2a-b) will use outcomes related to the longitudinal change in various metrics of glycemic variability (MAGE, C_v , range) as well as the frequency of hypoglycemic events, healthcare utilization, and cost. The secondary analyses will also use longitudinal data analysis to assess whether there is a significant reduction in glycemic variability over six months (Aims 1b-d) among those randomized to CGM, whether there is a significant reduction in hypoglycemic events over six months (Aim 1e) among those randomized to CGM, and to assess whether overall healthcare utilization and costs differ between randomized groups [9]. Accordingly, specific aims 1b-e will rely heavily on longitudinal data analysis within a multilevel/hierarchical framework [10], specifically using generalized linear mixed models. In the sensitivity analyses, provider variability will be accounted for using three-level (provider, patient, occasion), quasi-Bayesian generalized linear mixed models [11]. Finally, the sensitivity analyses exploring HTE will use generalized additive models (GAM) to identify subgroups of patients for whom CGM is likely to have a differential effect [12-13].

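### Section 7.1 words Aim 1e (hypoglycemic events) as a reduction within the CGM arm, in conflict with the between-arm comparison set out in Sections 2.0 and 7.0

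*Combined protocol and SAP*

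**What the plan says.** **Section 2.0, Specific Aim 1e.** The aim is titled "Measure the effect of CGM vs. the standard finger-prick protocol on frequency of hypoglycemic events". Its hypothesis is comparative: the "reduction in frequency of hypoglycemic events will be greater among those randomized to CGM than that among those randomized to control". The process fits a non-homogeneous Poisson process to each patient's events and takes the linear slope of the intensity λ over six months. Then: "Once we’ve computed each patient’s six-month linear change in λ , we will compare the distributions between randomized groups". The slope was chosen so that arms monitored in different ways can be compared. No test is named for that comparison.

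**Section 7.0.** The CGM-only variability aims (1b to 1d) are set apart as within-patient analyses. The remaining quantitative secondary aims are described as "the intervention effect on hypoglycemic events, healthcare utilization and cost (Aims 1e, 2a-b) between randomized groups". The section closes its overview with "Technical details are provided in Section 7.1".

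**Section 7.1.** "The secondary analyses will also use longitudinal data analysis", and one question it is to answer is "whether there is a significant reduction in hypoglycemic events over six months (Aim 1e) among those randomized to CGM". In the same sentence, Aims 2a and 2b keep a comparative form: "to assess whether overall healthcare utilization and costs differ between randomized groups". The next sentence assigns Aims 1b to 1e to generalized linear mixed models.

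**The concern.** One aim has two descriptions that ask different questions, and nothing ranks them. Aims 1b to 1d are confined to the CGM arm for a stated reason: their metrics need near-continuous readings. That reason does not carry over to Aim 1e, for which Section 2.0 builds a measure meant to work in both arms.

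A fall in events within the CGM arm mixes any effect of CGM with whatever else lowers event rates during the study. Several influences reach both arms. Everyone receives a device and supplies (Section 3.0), coordinators check in monthly (Section 4.2), and controls are given a study meter (Section 3.0). Only the randomized comparison removes what the arms have in common. With the choice left open, it could also be made after the data are seen.

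**Working it through.** **1. The descriptions side by side.**

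| Place | Aims 1b to 1d | Aim 1e | Aims 2a, 2b |
|---|---|---|---|
| Section 2.0 | CGM arm only | between arms | between arms |
| Section 7.0 | CGM arm only | between arms | between arms |
| Section 7.1 | CGM arm only | **CGM arm only** | between arms |

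Only the Aim 1e entry changes.

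**2. The plan's own figures.** There is no event rate, slope SD, power or significance level for Aim 1e, so there is nothing to reproduce for it. The sample size in Section 7.2 concerns HbA1c and reproduces: 100/(1 − 0.20) = 125 enrolled. At d = 1/1.25 = 0.8 with 50 per arm and two-sided 0.05, power is 97.9%, which meets the stated figure of more than 80%. It says nothing about Aim 1e, but it supplies the 100 analysed patients used below.

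**3. What a within-arm test does under a shared decline (illustrative).**

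Inputs:
- 100 analysed (Section 7.2). Equal allocation is assumed because no ratio is stated, giving 50 per arm.
- Two-sided 0.05, assumed.
- Per-patient slopes have the same distribution in both arms, with mean −s in SD units. There is therefore no CGM effect. The values of s are assumptions.

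The chance that the one-sample test in the CGM arm finds a significant reduction is approximately

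P = Φ(s·√50 − 1.96), with √50 = 7.071.

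For s = 0.2: 0.2 × 7.071 − 1.96 = −0.546, and Φ(−0.546) = 0.293.

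The formula was checked with 4,000 simulated trials per setting, using normal slopes, a one-sample t test in the CGM arm and a rank-sum test between arms.

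| Shared decline s (SD) | s·√50 − 1.96 | Within CGM, formula | Within CGM, simulated | Between arms, either direction | Between arms, favouring CGM |
|---|---|---|---|---|---|
| 0 | −1.960 | 2.5% | 2.6% | 4.2% | 1.8% |
| 0.2 | −0.546 | 29.3% | 28.7% | 4.6% | 2.5% |
| 0.3 | 0.161 | 56.4% | 53.5% | 4.8% | 2.2% |
| 0.5 | 1.576 | 94.2% | 93.8% | 5.3% | 2.8% |
| 0.8 | 3.697 | about 100% | about 100% | 4.8% | 2.4% |

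The direction does not depend on the inputs: any shared decline raises the within-arm rate, while the between-arm rate stays near nominal. The size depends on them entirely.

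**The case against.** The best defence is that Section 7.1 adds an analysis and replaces nothing. It says the secondary analyses will *also* use longitudinal methods, and Section 7.0 opens by announcing evaluation both between and within arms. The Aim 1e process in Section 2.0 is more detailed than the phrase in Section 7.1 and is nowhere withdrawn. An analyst would have to set aside the hypothesis, the process and Section 7.0 to report one arm alone.

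This has weight but does not settle the matter. In the same sentence Section 7.1 restates the main question for Aims 1b to 1d and for 2a and 2b, so the Aim 1e clause reads as its main question too. Section 7.0 goes on to say which aims are within-patient and which are between-arm, and it puts Aim 1e among the latter. Because Section 2.0 names no test for Aim 1e, a reader will turn to Section 7.1 for one and find the single-arm wording.

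A reader might infer something stronger: that the plan will declare a CGM benefit from a decline common to both arms, or that it abandons randomization for this aim. The documents do not support that. The between-arm comparison still stands in Section 2.0, the additive reading is possible, and no text makes a within-arm decline a criterion for benefit.

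The figures are also open to fair criticism. They show the power of a one-sample test against assumed declines, and a t test on normal slopes is not the mixed model of Section 7.1. The reassuring between-arm rate assumes the same slope distribution in both arms. Continuous and daily monitoring may detect events differently, and then an equal proportional decline would give unequal absolute slopes of λ.

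**Conclusion.** The inconsistency is real and should be resolved before analysis. Section 7.1 conflicts with Section 2.0 and Section 7.0 on whether Aim 1e is a within-arm or a between-arm question, and the within-arm version cannot test the stated hypothesis. The supported consequence is conditional: if Section 7.1 is followed alone, a shared decline *could* be reported as a CGM benefit. The rates of about 29% to nearly 100%, for shared declines of 0.2 to 0.8 SD, are illustrations. They rest on an assumed 50 per arm, an assumed two-sided 0.05, normal slopes and assumed declines, and they do not forecast this trial. The point is confined to one secondary aim of a study that calls itself a pilot, and the primary HbA1c analysis is untouched.

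**What to change.** Amend Section 7.1 in three respects.

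1. Restate Aim 1e as asking whether the six-month change in hypoglycemic event frequency differs between the randomized arms, and place it with Aims 2a and 2b.
2. Name the test, in agreement with the Aim 1e process in Section 2.0. One option is a rank-sum test on the per-patient slopes of λ. Another is an arm-by-time term in the mixed model that Section 7.1 already assigns to Aims 1b to 1e. Choose one in advance: the first compares absolute slopes, while the second compares relative change if a log link is used. Adjust the sentence on mixed models to match the choice.
3. Keep the CGM-arm trend if wanted, labelled as a supplementary within-arm result that is not used as evidence of a CGM effect.

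The cost is a few sentences in the analysis section. No extra data, patients or visits are needed. This change does not deal with any difference in event detection between the two monitoring methods.

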7.2 Sample Size and Power

Based on 2018 data pulled from Intermountain's diabetes registry, we estimate that the four RPC clinics (Cottonwood FM, Cottonwood Sr, Holladay IM, and Avenues IM) will see about 30, 22, 17, and 6 study-eligible, unique patient encounters per month, respectively, yielding up to about 75 recruitable patients per month (up to 225 over three months of enrollment). We estimate that enrolling 125 patients – expecting 20% attrition by the sixth-month follow-up, yielding 100 patients for analysis – would be sufficient to achieve >80% power for the primary analysis (absolute reduction in HbA1c) if the standardized difference d of the effect size is >0.8 (**Figure 2**). Here, the standardized difference d is measured in terms of the difference between the randomized group-level means of six-month changes in HbA1c. So, for example, a standardized difference d in the effect size of 0.8 might be observed if the true effect size is, say, -1 (that is, if the difference between the means is -1) and the standard deviation of change is 1.25. Details of the power analysis will be made available upon request.

[figure not shown]
8.0 DISSEMINATION OF RESULTS

There are no current plans for dissemination of study results to participants of this study. Should this change, IRB approval will be obtained prior to use of any method for study progress information dissemination to participants.

8.1 Release of Information to Participants

Whenever possible within the limits of the study, effort will be made to keep study participants informed of significant study results. This will mainly be a 1:1 discussion between the subject and their Primary Care Physician, as appropriate. Dissemination of results to the study participants will be performed only insofar as specific tests are performed by a clinical resource, such as a clinical laboratory or clinical testing department. All other results will be considered for research only and will not be shared with the individual subject directly.

Figure 2

Contour plot of power surface for the primary analysis (six-month change in HbA1c) as a function of total enrolled and remaining at six months (N) and standardized difference of the effect size (d).

8.2 Public Release of Information

IRB approval will be obtained prior to use of any method for information dissemination to the public (if there is a policy in place by that point in time). Otherwise methods of disseminating study results and/or study progress to the public may include press releases, publications, conference abstracts, etc.

Requests for interviews, comments, or press conferences with the study investigators will be honored to more fully describe the results or explain the implications of the results, following consultation with the Intermountain public relations team. Any direct request to the investigators will be sent to the Communications team first, before the investigator responds to the media request.

8.3 Data-Sharing with Collaborators

Deidentified data obtained from this study will be shared with Savvysherpa in accordance with signed legal documents to help develop predictive models for diabetes care. Data will be transferred using either SFTP or an encrypted hard drive and in accordance with cybersecurity approval.

Further, collected data will be transcribed into visualizations on a Tableau dashboard. The specific outputs will include recruitment totals for each particular site, patient demographics, glucose tracking, etc. No protected health information will be on the Tableau dashboard—it will serve as a real-time tracking tool for Intermountain senior leadership. Furthermore, [name], who specializes in diabetic management will be provided the dashboard link and he will interpret the CGM profiles on an interim basis. [name] will monitor subject safety within the data (Tableau) and report back any concerning findings to the study team and/or their respective Reimagine Clinic Provider. He will also regularly speak with the study team on his glucose monitoring results and data updates on a weekly basis.. This will ensure the safety of participants and be useful for developing future national standards on CGM diabetic care.

8.4 Publications

The results of this study may be published as a paper, abstract or poster, or may be presented orally at a conference or symposium. Any publication resulting from this study will comply with the guidelines recommended by the International Council of Medical Journal Editors (i.e., Recommendations for the Conduct, Reporting, Editing, and Publication of Scholarly Work in Medical Journals, 2013).

Opportunity will be given for Savvysherpa to also review the content and the conclusions drawn before the abstracts, papers or visual presentations are finalized, in accordance with the clinical research contract.

9.0 FINANCIAL CONSIDERATIONS

9.1 Funding Source

This project will be internally funded through the Business Development group at Intermountain Healthcare.

9.2 Compensation

Subjects will not receive any monetary or other forms of compensation for participating in this research study. Likewise, the investigators and their research staff will not receive any monetary or other forms of direct compensation for conducting this research study. Subjects who receive the Contour Next ONE will be asked to mail the device back to The Business Development Department at Intermountain Healthcare in a prepaid mailing envelope supplied to the patient upon study completion to ensure no compensating factors took part in the research study.

9.3 Disclosure of Conflicts of Information

The Principal Investigator, Co-Principal Investigator, Sub-Investigators and protocol authors declare that they have no conflicts of interest relevant to this study.

12.0 APPENDIX A

This section provides the questions which will be entered into REDCap and patients asked to complete at the end of the CGM study. There will be branching logic used based on the specific group assigned.

- 1. Which group were you assigned to?**
 - a. Group 1 (Dexcom G6)
 - b. Group 2 (ContourNext One)
- 2. What was the main reason that you signed up for this trial? _____.**
- 3. What was your biggest concern when you considered participating in this trial? _____.**
- 4. Were you initially disappointed with your group assignment?**
 - a. Yes
 - b. No

4b. Why were you disappointed with your group assignment? _____.
- 5. (For Group 1 participants): Did the Dexcom G6 impact your glucose management? For example, did it change your diet?**
 - a. Yes
 - b. No
- 6. (For Group 1 participants): Did the Dexcom G6 impact your glucose management? For example, did it change your exercise regimen?**
 - a. Yes
 - b. No
- 7. How did Dexcom G6 impact your glucose management? _____.**
- 8. (For Group 1 and 2 participants): On a scale of 1-5, where 1 is not helpful and 5 is extremely helpful, how would you rate the device?**
- 9. (For Group 1 and 2 participants): On a scale of 1-5, where 1 is extremely poor and 5 is extremely healthy, how would you rate your health BEFORE starting this study?**
- 10. (For Group 1 and 2 participants): On a scale of 1-5, where 1 is extremely poor and 5 was extremely healthy, how would you rate your health AFTER starting this study was completed?**
- 11. (For Group 2 participants): Did the ContourNext One impact your glucose management? For example, did it change your diet?**
- 12. (For Group 2 participants): Did the ContourNext One impact your glucose management? For example, did it change your exercise regimen?**
- 13. How did the ContourNext One impact your glucose management? _____.**
- 14. Did your glucose levels decrease between the initial enrollment and the end of the study? (Suggest inserting this filter question.)**
 - a. They increased
 - b. The decreased

c. No change

15. Would you be willing to participate in future Intermountain pilots in your primary care clinic? a.

Yes

b. No

16. General Comments. In the space provided, please feel free to add any other comments regarding your participation in this study. _____.

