Randomization will be assigned *a priori* using a random number generator from Microsoft Excel. Sub-Investigator will then transcribe these numbers and order them individually in concealed envelopes and present them to the Research Coordinators to ensure the CRC is blinded. At time of consent the Research Coordinator will hand the patient the earliest numbered envelope to randomize. . Patients in both randomized groups will be given the devices and one month supplies to ensure compliance with the protocol. The Study Coordinator and patient will exchange contact information so that the CRC may resupply the patient with necessary equipment at the end of their month supply. The CRC may meet the patient at their Reimagine Care Clinic or off site for patient convenience. All patients are expected to participate for six months, which is near the minimum duration sufficient to measure clinically meaningful changes in hemoglobin A1c related to gradual behavioral changes (e.g., diet, exercise, insulin administration). Further, each patient will complete 2 mandatory blood draws and one elective blood draw at their designated Reimagine Care Clinic to evaluate HbA1c level changes over the course of the study. Baseline HbA1c must be completed on day of enrollment (± 2 days) which Intermountain Healthcare may choose to cover if not paid for by patient's SOC. An elective blood draw will be considered for data if completed at 3 months (± 1 week) and a third required blood draw upon study completion (± 2 weeks) which the study may also choose to cover if not SOC. 2 weeks from 180 enrollment) which the study may pay for if not covered by patient's SOC. We postulate that those that have a more consistent interstitial glucose profile (which avoid the high peak to valley swings), will have a more pronounced difference in pre and post HbA1c levels. Specific Aim #1 above will help our team understand the relationship between interstitial glucose and HbA1c, along with other outcomes of interest which include weight loss, alterations in diet, change in physical activity, etc.

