3.3 Screening and Selection of Subjects

Subjects will be screened and recruited by Research Coordinators with CITI/HIPAA training. These coordinators will be trained in advance by Drs. [name] and [name], on how to instruct patients of proper usage of their device, how to effectively interact with subjects, the questions that may be posed, how patients should interpret feedback from the devices/cellphones, etc. [name] will also consult with the providers so that they understand the questions that may be asked by the patients and how to provide best care practices.

If a patient agrees to participate, a consent form will be electronically signed using REDCap. Participants will receive a paper copy of the consent containing all relevant and study pertaining information including important contact information. The subject will then be randomized into a study group and given the appropriate device by a Research Coordinator. Each patient will download the mobile apps relevant to their group, so their data can be tracked and transmitted by the study team.

- Group #1 will download the Dexcom G6 and Clarity apps
- Group #2 will download the Contour Next ONE Diabetes application.
- Both groups will also use REDCap to complete the end of study survey (**Appendix A**).

All devices will be registered prior to study startup and will be matched to a deidentified subject identifier (e.g. Subject_001). The coordinators will answer any study related questions that the patients may have before and during the study along with the Reimagine Primary Care clinicians who have agreed to participate as collaborators during the patient's regular appointments. Before patient's leave the clinic, (or ± 2 days) a blood draw will be conducted at the Reimagine site by a certified phlebotomist or approved healthcare provider to collect initial HbA1c level.

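### Exit-survey items 5/6 and 11/12 join a general question to a diet or exercise example, so a Yes cannot be read as a diet or exercise change

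*Combined protocol and SAP*

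**What the plan says.** Appendix A lists the end-of-study questions to be entered in REDCap. For Group 1 (CGM), item 5 reads "Did the Dexcom G6 impact your glucose management? For example, did it change your diet" and item 6 reads "Did the Dexcom G6 impact your glucose management? For example, did it change your exercise regimen". Each is followed by one Yes/No. For Group 2 (finger-prick), item 11 reads "Did the ContourNext One impact your glucose management? For example, did it change your diet" and item 12 reads "Did the ContourNext One impact your glucose management? For example, did it change your exercise regimen". No response options appear under items 11 and 12 in the text available, which may be an omission or a loss in reading the PDF. Items 7 and 13 then ask in open text how the device affected glucose management.

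Three places give these items a purpose:

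- Section 3.0 speaks of "other outcomes of interest which include weight loss, alterations in diet, change in physical activity, etc".
- The synopsis lists self-reported behavioral changes among the secondary endpoints.
- Aim 3c (Section 2.0) is about how CGM changed patient behavior. It plans 5-point Likert questions, to be summarized for investigators and operational leaders.

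On the arm, item 1 asks "Which group were you assigned to" and prints the device name beside each option. The appendix introduction says "There will be branching logic used based on the specific group assigned". Section 3.3 says of the devices that they "will be matched to a deidentified subject identifier".

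**The concern.** Items 5 and 6 open with the same broad question, and diet or exercise enters only as an example of it. An example illustrates a question and does not limit it. A patient who changed insulin use and nothing else can truthfully answer Yes to both. A patient who changed only diet can truthfully answer Yes to the exercise item. Neither item records the direction of a change.

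These are the only closed questions on diet and exercise in the survey, and the plan describes no other instrument for those outcomes. A table of diet and exercise changes built from them would be hard to interpret. Once the answers are in, no analysis can separate patients who answered the opening question from patients who answered the example. Aim 3c intends the results to inform clinical operations, so a misread proportion could be acted on.

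**Working it through.** The plan gives no figure for these items, so there is none to reproduce. The check is a comparison of wording, followed by a short calculation to show scale.

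**Wording.** How three kinds of CGM patient could answer items 5 and 6 under each reading:

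| What the patient changed | Answers the opening question (items 5, 6) | Answers the example (items 5, 6) |
|---|---|---|
| Insulin use only | Yes, Yes | No, No |
| Diet only | Yes, Yes | Yes, No |
| Diet and exercise | Yes, Yes | Yes, Yes |

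Under the first reading the two items carry the same information and neither identifies diet or exercise. Under the second they work as presumably intended. The survey does not show which reading a patient used. Cross-tabulating item 5 against item 6 helps only if each patient read both items the same way. The insulin row is not contrived: Section 3.0 names insulin administration alongside diet and exercise as a gradual behavioral change that moves HbA1c. The same table applies to items 11 and 12.

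**Scale.** Inputs:

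- Analyzable patients: 125 × (1 − 0.20) = 100 (Sections 3.2 and 7.2).
- Per arm: 100 / 2 = 50, assuming 1:1 allocation and that these patients also complete the survey.
- Share y answering Yes to item 5: not in the documents, so shown as a range.

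Assume that anyone who changed diet counts that as an impact and says Yes. The diet-change share is then at most y. It equals y if everyone answered the example, and it can be as low as 0 if everyone answered the opening question. The sampling half-width is 1.96 × √(y(1 − y)/50).

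| y (assumed) | Diet-change share consistent with the data | Sampling half-width |
|---|---|---|
| 0.3 | 0 to 0.3 | 1.96 × √(0.21/50) = 0.127 |
| 0.5 | 0 to 0.5 | 1.96 × √(0.25/50) = 0.139 |
| 0.7 | 0 to 0.7 | 1.96 × √(0.21/50) = 0.127 |

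In each row the ambiguity range is wider than the full sampling interval (0.25 to 0.28). Enrolling more patients would narrow the sampling error and leave the ambiguity unchanged.

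**Reach.** Aim 1a uses laboratory HbA1c and the power statement in Section 7.2 concerns HbA1c only. Neither draws on the survey.

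**The case against.** The strongest reply is that few patients parse a question so literally. Items 5 and 6 differ only in their last sentence, so many patients will treat diet or exercise as the question. Items 7 and 13 then let them explain, including the direction of change and any insulin adjustment. Aim 3 is headed as qualitative, no analysis of diet or exercise proportions is specified, and item 14 still carries a drafting note, so the form may not be final.

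Much of this stands. It is why the proportions should be called uninterpretable and possibly overstated, not shown to be inflated. It does not remove the fault. The mix of readings is unknown, each free-text item is a single open question about the device overall, and the plan gives no coding scheme for the answers. An unfinished form is also the cheapest one to correct.

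Two stronger readings are tempting and should not be drawn:

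- **Misrouting.** A reader might infer that self-report in item 1 sends patients down the wrong branch, and that item 1 should go because REDCap already knows the arm. The documents support neither step. Branching follows the assigned group, with no driving field named. Patients know which device they used, and item 1 names it. No section says that the allocation is held in REDCap; Section 3.3 says only that devices are matched to a subject identifier. Section 3.0 speaks of a survey link without saying that it is participant-specific. If it is not, deleting item 1 could lose the arm from the survey data.
- **A multiple.** A reader might want to state by what factor diet or exercise change is overstated. That needs the true shares and the proportion of literal readers, and the documents give neither.

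**Conclusion.** The point holds as a wording fault of limited reach. Items 5 and 6 ask two things under one Yes/No, and items 11 and 12 repeat the two-part wording, although their response format is not shown. A Yes cannot be read as a diet or exercise change, and the direction of any change is not recorded in the closed items.

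The size is an identification range of 0 to y for a Yes share y. It rests on the assumption that patients who changed diet (or exercise) answer Yes, and on no knowledge of how patients read the item. The comparison with sampling error also assumes 50 completers per arm. Items 7 and 13 may narrow the range, by an amount that cannot be stated in advance.

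The effect is confined to descriptive results: Aim 3c, the secondary endpoint of self-reported behavioral changes, and the diet and physical activity outcomes of interest. The HbA1c analysis and the sample size are untouched. The change is desirable, not essential.

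**What to change.** Before the survey is deployed, replace each pair (5/6 and 11/12) with three items, identical in both arms except for the device name and with the same printed response options:

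- (a) Did the device affect how you manage your glucose? Yes / No.
- (b) Did using the device change your diet, and if so in which direction?
- (c) Did using the device change your physical activity, and if so in which direction?

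This wording keeps the attribution to the device that the present items ask for. A question about any change since joining the study would measure something else.

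Keep items 7 and 13 as follow-ups. Keep item 1, but analyze survey results by the randomized arm in the study record.

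The cost is minor rewording, one more closed item per arm, and IRB acknowledgement of the revised survey. No visits are added. The drafting note in item 14 can be cleared in the same revision.
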